13.1.2. Safety analyses

All safety endpoints will be evaluated on subjects who receive at least 1 dose of investigational product (SZC or placebo).

13.2. Missing data

All endpoints will be analyzed on a complete case basis, on all subjects with available data for the endpoint being analysed. The level of missing data (number and percentage) will be presented for each endpoint by the trial group.

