### 13.8.2 Schedule of Assessment (in Diagrammatic Format) and protocolised dosing management of IMP

Schedule of visits	Screening	Visit 1	Visit 2	Visit 3	Visit 4	Visit 5	Visit 6	Visit 7	follow up visit	Unscheduled	Early termination visit
Day	Day - 14 to - 7	Day 0	Day 7 (+/-2)	Day 14 (+/-4)	Day 28(+/-4)	Day 42 (+/-4)	Day 56(+/-4)	Day 84(+/-4)	Day 98 (+/-4)		
Informed Consent	X										
Eligibility criteria	X	X									
Demographic data	X										
Medical history	X										
Pregnancy test if WOCBP	X										
Concomitant medication	X	X	X	X	X	X	X	X	X	if needed	X
Randomisation		X									
Stop background antihypertensives	X										
First IMP dose at site		X									
Drug accountability (IRB and SZC)			X	X	X	X	X	X		If needed	
IMP and NIMP drug dispense			X		X		X			If needed	
Physical examination	X	X	X	X	X	X	X	X	X	If needed	X
Vital signs	X	X	X	X	X	X	X	X	X	If needed	X
FBC		X						X		If needed	
U+E (+bicarbonate)	X	X	X	X	X	X	X	X	X	If needed	X
Pro NT BNP		X						X			
Optional POC potassium		X	X	X	X	X	X	X			
ECG	X	X	X	X	X	X	X	X	X	If needed	X
Urine collection (uACR)		X						X		If needed	
AE assessment		X	X	X	X	X	X	X	X	X	X
Uptitration of RASI			X	X	X	X	X	X		If needed	

RASI dose back to baseline							x				x
-----------------------------------	--	--	--	--	--	--	----------	--	--	--	----------

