12. POWER CALCULATION

From published data, reduction in serum potassium with SZC is between 0.7-1mmol/l. From this data we hypothesise that 30% of patients on placebo will get to maximum dose of irbesartan (300 mg) and double the number of patients (60%) on irbesartan will get to maximum dose of irbesartan by the end of the study (12 weeks). Under these assumptions, the sample size calculation using a 2-sided Chi-square test at the 5% level of significance, with 80% power to detect the assumed difference, led to a total sample size of 98 patients (49 in each trial group).

We envisage reasons for possible patient drop-out from the trial to be either a result of a decline in eGFR or hypotension. Assuming a 15% drop-out rate, we inflate the sample size to 116 patients (58 in each trial group).

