15.2.2. Change in blood pressure levels over the trial

The change in office BP from baseline to the end of the trial (12 weeks) will be calculated as the difference between baseline and end of trial BP. This analysis will be repeated for systolic and diastolic BP.

Mean office BP at baseline and at the end of the trial will be calculated as the mean of the 2nd and 3rd office readings for each occasion. If only 2 readings were recorded, the mean of those 2 will be used. If only 1 reading was recorded, then that lone recording will be used. Mean BP at baseline and the end of the study will be calculated separately for SBP and DBP.

15.2.3. The mean change in BP will be presented by treatment group. Experiencing an adverse event during the trial

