15.2.6. Change in eGFR over the trial

The change in eGFR from baseline to the end of the trial (12 weeks) will be calculated as the difference between baseline and end of trial BP. The mean change in eGFR will be presented by treatment group.

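### The complete-case week-12 means for eGFR and BP can understate the fall within each arm, because the SAP expects some patients to leave the trial for those same reasons

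*SAP*

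**What the plan says.** SAP 13.2 sets one missing-data rule for every endpoint: "All endpoints will be analyzed on a complete case basis, on all subjects with available data for the endpoint being analysed". SAP 13.1.1 says the same. SAP 13.1.2 defines the safety set as everyone who took at least one dose, and 13.2 then reduces it to those with data. The only safeguard in 13.2 is a count and percentage of missing data by group.

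On why patients leave, SAP 12 says: "We envisage reasons for possible patient drop-out from the trial to be either a result of a decline in eGFR or hypotension". It adds a 15% allowance, which raises 98 patients to 116.

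Both endpoints run from baseline to week 12. For eGFR (SAP 15.2.6): "The mean change in eGFR will be presented by treatment group". For BP (SAP 15.2.2): "The mean change in BP will be presented by treatment group". Table 5 in SAP 16 adds a mean difference with a 95% confidence interval.

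The schedules in protocol 13.8.2 and SAP 11 collect U+E and vital signs at every visit, including a column headed "Early termination visit". Protocol 19.11 says that missing outcome data will prompt a sensitivity analysis. SAP v1.1 contains none.

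**The concern.** On the SAP's own account, the reason a week-12 eGFR or BP value is missing can be that eGFR or BP fell. Missingness then depends on the variable being averaged, and the mean of those who remain is tilted towards no harm. These are safety summaries of raising irbesartan to its maximum dose, so a reader would take them as evidence that renal function and BP held up. The number missing shows that patients are absent, but not that their last values were poor. Those values are on the schedule, yet no mean-change analysis uses them for a patient who left. The point concerns the safety endpoints, not the primary endpoint.

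**Working it through.** **1. The plan's own figure.** Inputs: 60% and 30% reaching 300 mg (protocol 19.1, SAP 12), 1:1 allocation (protocol 11.6), and a calculation "using a 2-sided Chi-square test at the 5% level of significance, with 80% power to detect the assumed difference".

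- Uncorrected n per arm = [1.960 × √(2 × 0.45 × 0.55) + 0.842 × √(0.24 + 0.21)]² / 0.30² = 41.97, so 42 (84 in total).
- With continuity correction, n per arm = (41.97/4) × [1 + √(1 + 4/(41.97 × 0.30))]² = 48.4, so 49 (98 in total). This matches the SAP.
- 98/0.85 = 115.3, so 116. This also matches.

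The 15% is therefore a working allowance for patients without an outcome: 0.15 × 58 = 8.7 per arm at the planned size.

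**2. Shift in one arm's mean.** Let d be the share missing, C the completers' mean change and L the leavers'. The full mean is (1 − d)C + dL, so the completer mean exceeds it by d × D, where D = C − L. The documents give no D, so these values are assumed.

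- eGFR: leavers fell by 30% of baseline more than completers. Over the entry range of 25-60 ml/min, D = 0.30 × 25 = 7.5 to 0.30 × 60 = 18 ml/min. At d = 0.15 the fall is understated by 1.1 to 2.7 ml/min.
- BP: D = 10 to 30 mmHg. At d = 0.15 the fall is understated by 1.5 to 4.5 mmHg.

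**3. Shift in the between-arm difference.** This is d(SZC) × D(SZC) − d(placebo) × D(placebo). With equal D in both arms:

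| Missing, SZC / placebo | eGFR difference (ml/min) | BP difference (mmHg) |
|---|---|---|
| 15% / 15% | 0 | 0 |
| 20% / 10% | 0.75 to 1.8 | 1 to 3 |
| 25% / 5% | 1.5 to 3.6 | 2 to 6 |

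The splits by arm are assumptions.

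**4. Truncated-normal illustration for eGFR.** Assume percentage change is normal with mean m and SD s, and that a fraction q of patients with a fall above 30% leave. Let a = (−30 − m)/s, p = Φ(a) and L = m − s × φ(a)/p. The reported mean is (m − q × p × L)/(1 − q × p). When q = 1 this is m + s × φ(a)/(1 − p).

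Example with m = −15, s = 15, q = 1: a = −1, φ = 0.2420, p = 0.1587. Reported mean = −15 + 15 × 0.2420/0.8413 = −10.7. The understatement is 4.31/15 = 29%.

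| SD | Share of >30% fallers who leave | True mean (%) | Patients leaving | Reported mean (%) | Fall understated by |
|---|---|---|---|---|---|
| 15 | all | −10 / −12 / −15 | 9% / 12% / 16% | −7.3 / −8.7 / −10.7 | 27% / 27% / 29% |
| 15 | half | −10 / −12 / −15 | 5% / 6% / 8% | −8.7 / −10.5 / −13.0 | 13% / 13% / 13% |
| 10 | all | −10 / −12 / −15 | 2% / 4% / 7% | −9.4 / −11.2 / −13.6 | 6% / 7% / 9% |

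The SD, the means and the leaving rule are all assumed. The first row is close to a worst case.

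**5. What other outputs catch.** SAP 15.2.5 counts any eGFR fall above 30% between one visit and the next, so a steep fall before leaving can still be recorded. A stepwise fall may not be: two successive 20% falls leave 0.8 × 0.8 = 0.64 of baseline, a 36% loss that is not counted. BP has no threshold or any-visit endpoint. Protocol 17.6 exempts potassium, BP and creatinine changes from AE reporting unless tied to an SAE or an AE of special interest, and protocol 17.5 limits the latter to potassium levels.

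**The case against.** The strongest reply is that few patients may be affected. Protocol 13.9 keeps patients who stop IMP in the visit schedule, and anyone who attends week 12 is in the mean. Protocol 19.1 mentions drop-outs for eGFR change or hypotension while explaining why only 60% would reach the top dose, which may mean failed titration with follow-up intact. SAP 12 turns this into drop-out from the trial. This stands: the concern applies only to patients who leave the visits, and the two sections need reconciling. It does not remove the point, because protocol 13.9 and 13.10 let patients decline further visits and SAP 12 plans for drop-out from the trial. Routine clinical data (13.9) or GP records (19.11) might supply a late value, but the SAP does not say that it would be used.

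A reader might infer that these harms vanish from the report. They do not: the >30% eGFR endpoint, the withdrawal reasons (SAP 14) and the AE and SAE outputs (SAP 15.2.3) can show some of them. A reader might also infer that the SZC-placebo difference is biased towards no harm. That is plausible if more SZC patients are titrated up and then leave, but no arm-specific drop-out or gap is given, and with equal drop-out and equal gaps the distortion is zero.

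For BP even the direction is not assured. Background antihypertensives are generally stopped at screening (protocol 13.8.3), so some patients may leave because BP is high.

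Finally, the trial closed early and SAP 13.3 drops hypothesis testing, which lowers the stakes. However, Table 5 still reports mean differences with confidence intervals, and in a small sample each omitted extreme value moves a mean more.

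**Conclusion.** The point holds in a limited form. For patients with no week-12 value, the stated rule and the stated reasons for leaving together make missingness depend on the outcome, so the within-arm week-12 means can understate the fall. The size cannot be fixed from the documents: they give no SD, no mean change and no leaver-completer gap, and the obtained sample size is not stated. The illustrations range from about 6-9% to about 27-29% of the eGFR fall, and the upper figure should not be read as an estimate. Distortion of the between-arm difference is a possibility, not a finding. Cover is weakest for BP, where the week-12 mean is the only dedicated summary. This is an inexpensive improvement to a descriptive analysis and does not invalidate the safety tables.

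**What to change.** - In SAP 13.2, 15.2.2 and 15.2.6, keep the week-12 complete-case mean. Add the descriptive change from baseline to the last available on-study value, including the early termination visit, for all dosed patients by arm. Label it as the sensitivity analysis that protocol 19.11 promises.
- For each patient with no week-12 value, list the last eGFR and BP, the visit they come from and the reason for leaving.
- Reconcile protocol 19.1 and SAP 12 on whether drop-out means failed titration or leaving the trial.

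A lowest post-baseline value is not a good main alternative. It depends on how many visits a patient attended, and it mixes harm with the acute eGFR fall that protocol 9.1 expects.

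The cost is SAP wording, a few extra rows in Table 5 and one listing, all from data already on the schedule. The drawback is that last values come from different visits, so the added rows mix short and long exposure and should be read beside the week-12 mean.

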13.3. Level of significance

Hypothesis testing will not be carried out due to the small obtained sample size. .

13.4. Covariate adjustment

Covariate adjustment will not be utilised due to the small obtained sample size.

13.5. Assumptions for analysis

Continuous endpoints will be assessed for normality visually using histograms. This assessment will inform the data presentation/analysis.

The data will be assessed for unrealistic values. If any continuous endpoints are considered to be unrealistic, they will be replaced with a missing value. If an endpoint is extreme but still considered possible, then it will be kept in the analysis.

13.6. Multiple comparisons

13.7. Hypothesis testing will not be performed meaning that no correction for multiple testing are necessary. Subgroup analysis

No subgroup analyses will be performed due to the small obtained sample size.

Interim analysis

No formal interim analyses are planned.

14. DEMOGRAPHICS AND BASELINE CHARACTERISTICS

Participants enrolled to the study will be described with respect to demographic data, medical history, and baseline vital signs. These descriptions will be presented separately by trial group and overall.

For continuous data, the number of subjects with data, the mean and SD (if normally distributed), median and interquartile range (if not normally distributed) will be presented. For categorical data, the number and percentage in each category will be presented.

The number of participants screened, the number excluded from participation (with reasons), the number randomised into each group, the number attending each scheduled visit, the number attending the final visit (at week 12), the number lost to follow-up, and the number assessed for the primary outcome will be shown in a trial flow diagram. The number and reasons for early withdrawal from both cohorts will be presented.

15. ANALYSIS OF OUTCOMES

15.1. Methods for analysis of the primary endpoint

The primary endpoint of the reaching the maximum dose of irbesartan (300 mg) at the end of the study (12 weeks) will be compared between trial groups. The number (and percentage) achieving the outcome will be presented in each trial group.

The number of subjects with no available data for the primary endpoint will be given.

15.2. Methods for analysis of safety endpoints

15.2.1. Change in potassium levels over the trial

The change in potassium level from baseline will be calculated for each scheduled trial visit (1 week, 2 weeks, 4 weeks, 6 weeks, 8 weeks, and 12 weeks).

15.2.2. Change in blood pressure levels over the trial

The change in office BP from baseline to the end of the trial (12 weeks) will be calculated as the difference between baseline and end of trial BP. This analysis will be repeated for systolic and diastolic BP.

Mean office BP at baseline and at the end of the trial will be calculated as the mean of the 2nd and 3rd office readings for each occasion. If only 2 readings were recorded, the mean of those 2 will be used. If only 1 reading was recorded, then that lone recording will be used. Mean BP at baseline and the end of the study will be calculated separately for SBP and DBP.

15.2.3. The mean change in BP will be presented by treatment group. Experiencing an adverse event during the trial

15.2.3.1. Adverse events (AEs)

AEs will be summarised using counts and percentages, separately by treatment group and overall. The number of subjects having at least one AE will be presented. The number of subjects with AEs of mild/moderate/severe intensity will be presented. The number of subjects with an AE at least possibly related to trial treatment (S2C/Placebo) will be presented.

Adverse events will be tabulated by system organ class and preferred term, as well as by severity and causality as judged by the investigator.

15.2.3.2. Fatal and non-fatal serious adverse events (SAEs)

Deaths and non-fatal SAEs will be listed separately along with details of treatment for both treatment groups, and whether the event is unexpected and whether it is thought to be related to treatment.

15.2.4. Experiencing high or low levels of potassium during the trial

The number and proportion of subjects experiencing high levels of potassium (defined as 6 mmol/L or high) at any point during the trial, between baseline and the end of the trial (12 weeks) will be presented. In addition, the number and proportion of subjects experiencing low levels of potassium defined as levels lower than 3.5 mmol/L at any point during the trial.

15.2.5. Experiencing sudden large decline in eGFR during the trial

The number and proportion of subjects experiencing a decline in eGFR of more than 30% between any trial visit and the next (from baseline to the end of the trial at 12 weeks) will be presented.

[figure not shown]
15.2.6. Change in eGFR over the trial

The change in eGFR from baseline to the end of the trial (12 weeks) will be calculated as the difference between baseline and end of trial BP. The mean change in eGFR will be presented by treatment group.

16. PRESENTATION OF ANALYSIS

Results will be presented as follows.

Figure 1: Study flow diagram

- **Table 1: Demographics and baseline characteristics, by study cohort**

Table 2: Primary outcome – reaching maximum dose of irbesartan (300mg) at end of trial

Analysis population	Number (%)		Odds ratio (95% CI)
	SZC Group	Placebo Group	
Primary outcome	N (%)	N (%)	
	N (%)	N (%)	

Table 5: Safety endpoints (safety population) – continuous

Safety endpoint	Mean (SD)		Mean difference (95% CI)
	SZC Group	Placebo Group	
Change in potassium, mmol/L	(N=)	(N=)	
Change in blood pressure, mmHg	Systolic Diastolic	(N=)	(N=)
Change in eGFR, ml/min/1.73 m²		(N=)	(N=)

Table 6: Safety endpoints (safety population) – binary

Exploratory endpoint	SZC Group (N=)	Placebo Group (N=)	Odds ratio (95% CI)
Potassium higher than 6.5 mmol/L at any point during the trial			
Potassium higher than 6.0 mmol/L at any point during the trial			
Potassium lower than 3.0 mmol/L at any point during the trial			
Reduction in eGFR more than 30% from one trial visit to the next			

- **Table 10: Safety analysis (AEs, safety population)**
- **Table 11: Safety analysis (fatal and all SAEs, safety population)**
- **Table 12: SAE listing**

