#### 11.3.2 Safety Endpoints

- Change in potassium from baseline at each time point
- Change in the BP at the end of the study from baseline
- Frequency of adverse events
- Proportion of patients who have a K of >6, or >6.5 at any time during the study
- Proportion of patients who have a K of <3.5 at any time during the study
- Proportion of patients whose GFR falls by >30% from the previous test
- Change in (eGFR) renal function at the end of study from baseline

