## 11.5 Objectives and End Points Summary

Objective	How objective measured	outcome of measurement
Examine the ability of SZC to enable RASI (irbesartan) maximisation at 12 weeks	Dose of Irbesartan therapy at 12 weeks	Proportion of patients on Maximum dose Irbesartan therapy at the end of 12 weeks compared to placebo
Effect of SZC enabled RASI optimisation on potassium	lab potassium	Change in potassium from baseline at each time point
Effect of SZC enabled RASI optimisation on BP	clinic BP	change in BP between start and end of study
Examine the effect of SZC use on patient safety	SAE/AE	Frequency of adverse events
Effect of SZC enabled RASI optimisation on incidence of severe hyperkalaemia	lab potassium	Proportion of patients who have a K of >6, or >6.5 at any time during the study
Effect of SZC enabled RASI optimisation on incidence of hypokalaemia	lab potassium	Proportion of patients who have a K of <3.5 at any time during the study
Effect of SZC enabled RASI optimisation on incidence of AKI	eGFR	Proportion of patients whose GFR falls by >30% from the previous test
Effect of SZC enabled RASI optimisation on renal function	eGFR	Change in (eGFR) renal function at the end of treatment from baseline
Effect of SZC enabled RASI optimisation on markers of heart failure	lab BNP	change in pro BNP between start and end of treatment
Examine the ability of SZC to enable RASI (irbesartan) uptitration	Dose of Irbesartan therapy at each visit	Proportion of patients able to remain on 75/150/300mg dose of irbesartan at the end of treatment
Effect of SZC on enabled RASI optimisation on proteinuria	uACR	Ratio of uACR between baseline and 3-month study visit in patients treated with placebo versus SZC
Effect of SZC on enabled RASI optimisation on proteinuria	uACR	Absolute uACR at end of treatment

Effect of SZC on bicarbonate levels	Serum Bicarbonate	Change in serum bicarbonate levels between baseline and end of treatment
Effect of SZC on urea	Serum urea	Change in serum urea levels between baseline and end of treatment

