## 13.9

### IMP withholding criteria

The IMP will be withheld immediately and the patient will receive appropriate medical intervention, but continue in the study if:

- Potassium < 3.5 mmol/L, at any time during the study\*
- Potassium is found to be >6.5 despite not being on ARB any time during the study.
- If an absolute QTc(f) >550ms, or an increase in QTc interval > 60ms from baseline to more than 500ms is reached . All patients meeting the QTc(f)>500ms criterion should immediately have potassium assessed, if not already done within 1 hour of performing the ECG.
- If it is felt to be in the participant's best interest to stop the study treatment
- if the investigator feels that individual adverse events or IMP related side effects compromise the patient's safety or quality of life for example if the investigator feels that hyperkalaemia is a safety risk, then the IMP/or NIMP may be stopped and the patient treated as per local standard of care.
- In addition the patient may be brought up for an unscheduled visit to recheck potassium if felt to be clinically needed as per local practice
- The investigator feels that individual adverse events or new information gained mean that it is not safe to continue the study
- If the patient becomes pregnant.
- If the patient is found to be non-adherent to the study medication (see section 15.19)

If at a subsequent visit(s), and after appropriate management and if the withholding criteria are no longer present the PI may elect to reintroduce the IMP.

\*If a patient develops hypokalaemia (<3.5mmol/l) the IMP will be withheld and the patient will be managed as standard of care. The IMP can only be restarted if hypokalaemia has resolved and the serum potassium has risen to >5mmol/l. If hypokalaemia (serum K <3.5mmol/l) recurs on reintroducing IMP then IMP is permanently withdrawn.

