## 17.5 Notification of AEs of special interest

Potassium levels at any point >6.5mmol/l  
Any potassium level <3.5mmol/l

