8.2. Safety objectives

	Safety Objectives	Secondary Endpoints	Outcome measures
2.1	To compare the change in potassium levels over the trial between SZC and placebo groups.	Change in potassium from baseline to the time-point of each trial visit (1 week, 2 weeks, 4 weeks, 6 weeks, 8 weeks, and 12 weeks).	Mean difference in change in potassium from baseline to each trial visit between SZC and placebo groups.
2.2	To compare the change in BP over the trial between SZC and placebo groups.	Change in office BP (Systolic and diastolic) from baseline to the end of the trial (12 weeks).	Mean difference in change in BP from baseline to the end of the trial (12 weeks) between SZC and placebo groups.

2.3	To compare the proportion experiencing an adverse event during the trial between S2C and placebo groups.	Experiencing adverse events during the trial (to 12 weeks).	The difference in proportion of patients experiencing a adverse events between baseline and the end of the study (12 weeks) between S2C and placebo groups.
2.4	To compare the proportion experiencing high levels of potassium at any point during the trial between S2C and placebo groups.	Experiencing potassium levels higher than 6 mmol/L, and higher than 6.5 mmol/L at any point during the trial (to 12 weeks).	Difference in proportion of patients experiencing potassium levels higher than 6 mmol/L, and higher than 6.5 mmol/L at any point during the trial (to 12 weeks) between S2C and placebo groups.
2.5	To compare the proportion experiencing low levels of potassium at any point during the trial between S2C and placebo groups.	Experiencing potassium levels lower than 3.5 mmol/L at any point during the trial (to 12 weeks).	Difference in proportion of patients experiencing potassium levels lower than 3.5 mmol/L at any point during the trial (to 12 weeks) between S2C and placebo groups.
2.6	To compare the proportion experiencing sudden large decline in eGFR during the trial between S2C and placebo groups.	Experiencing a reduction in eGFR more than 30% from the previous visit test.	Difference in proportion of patients experiencing reduction in eGFR more than 30% from the previous visit test between S2C and placebo groups.
2.7	To compare the change in eGFR over the trial between S2C and placebo groups.	Change in eGFR from baseline to the end of the trial (12 weeks).	Mean difference in change in eGFR from baseline to the end of the trial (12 weeks) between S2C and placebo groups.

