10.2. Safety endpoints

Safety endpoints are:

- change in potassium from baseline to the time-point of each trial visit (1 week, 2 weeks, 4 weeks, 6 weeks, 8 weeks, and 12 weeks)
- change in office BP (systolic and diastolic) from baseline to the end of the trial (12 weeks)
- experiencing an adverse event during the trial (to 12 weeks)
- experiencing potassium levels higher than 6 mmol/L, and higher than 6.5 mmol/L at any point during the trial (to 12 weeks)
- experiencing potassium levels lower than 3.5 mmol/L at any point during the trial (to 12 weeks)
- experiencing a reduction in eGFR more than 30% from the previous visit test
- change in eGFR from baseline to the end of the trial (12 weeks).

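### SAP Table 6 is set up to count potassium below 3.0 mmol/L, although the hypokalaemia endpoint is below 3.5 everywhere else; SAP 15.2.4 also counts exactly 6.0 as high, although that endpoint is strictly above 6

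*SAP*

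**What the plan says.** **Low potassium.** Protocol 11.3.2 sets the safety endpoint as "Proportion of patients who have a K of <3.5 at any time during the study". Protocol 11.5 and 19.3 repeat the 3.5 threshold, and so do SAP 8.2 (row 2.5) and 10.2. The SAP's method section, 15.2.4, asks for the number and proportion with "low levels of potassium defined as levels lower than 3.5 mmol/L at any point during the trial". The same figure drives conduct and reporting in the protocol. Section 13.9 says "If a patient develops hypokalaemia (<3.5mmol/l) the IMP will be withheld", and section 17.5 lists "Any potassium level <3.5mmol/l" as an adverse event of special interest. The results shell in SAP section 16, Table 6, has a single low-potassium row: "Potassium lower than 3.0 mmol/L at any point during the trial".

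**High potassium.** Protocol 11.3.2, 11.5 and 19.3, SAP 8.2 and 10.2, and Table 6 itself all use strictly more than 6 mmol/L and, separately, more than 6.5. SAP 15.2.4 instead defines high potassium as 6 mmol/L and upwards, and does not mention 6.5.

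**Revision history.** SAP section 3 lists the version 1.1 changes: a change of statistician, a font change, and removal of the exploratory endpoints, the per-protocol analysis and hypothesis testing. No potassium threshold is mentioned.

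**The concern.** Protocol 9.2 names hypokalaemia as a risk of SZC. Table 6 is the only output shell that sets potassium-threshold counts side by side by arm, with an odds ratio. If it is programmed as drafted, a patient whose potassium fell to 3.2 would meet the prespecified endpoint, would have had study drug withheld under protocol 13.9, and would still not be counted in that row. The text of 15.2.4 and the table would then report different numbers for one endpoint, and nothing in the SAP says which governs.

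The 3.0 cannot be read as an additional severity tier. The high side has two rows (6.0 and 6.5), whereas the low side has only one, so 3.0 replaces the endpoint.

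The high-potassium wording raises the same question on a smaller scale. Exclusion criterion 19 bars randomisation only above 6, so a patient at exactly 6.0 is eligible. Because 15.2.4 counts from baseline, that patient could be scored as a high-potassium event on the baseline value.

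**Working it through.** **Step 1: compare the texts.** No figure in the documents has to be reproduced here; the contradiction is textual.

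| Place | Low threshold | High threshold |
|---|---|---|
| Protocol 11.3.2, 11.5, 19.3 | <3.5 | >6 and >6.5 |
| Protocol 13.9 (withholding study drug) | <3.5 | not compared |
| Protocol 17.5 (special-interest event) | <3.5 | not compared |
| SAP 8.2, 10.2 | <3.5 | >6 and >6.5 |
| SAP 15.2.4 | <3.5 | ≥6; 6.5 absent |
| SAP 16, Table 6 | **<3.0** | >6.0 and >6.5 |

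Table 6 is the only readable place that uses 3.0 as a potassium threshold, and 15.2.4 is the only place that makes the upper limit inclusive.

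**Step 2: who is misclassified.** If potassium is recorded to one decimal, the Table 6 row drops every patient whose lowest value is 3.0 to 3.4. The wording in 15.2.4 adds only patients whose highest value is exactly 6.0. One-decimal recording is inferred from the potassium bands in protocol 15.13 and is not stated.

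**Step 3: illustrate the size.** The documents give no potassium mean, SD, within-patient correlation or achieved sample size, so all of these are assumptions. The model takes potassium as normal, with six post-baseline visits to week 12 and no effect of withholding study drug. With rounding, a recorded value below 3.5 means a true value below 3.45, and below 3.0 means below 2.95.

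P(ever) = 1 − (1 − p)^6, where p is the probability at one visit.

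Hypokalaemia, mean 4.5 and SD 0.5, visits independent:
- Below 3.5: p = Φ((3.45 − 4.5)/0.5) = Φ(−2.1) = 0.0179, so P(ever) = 0.1025.
- Below 3.0: p = Φ((2.95 − 4.5)/0.5) = Φ(−3.1) = 0.00097, so P(ever) = 0.0058.
- Planned arm of 58: 58 × 0.1025 = 5.9 against 58 × 0.0058 = 0.3, so 5.6 patients are dropped.
- Assumed arm of 20: 2.1 against 0.1. The row is empty with probability (1 − 0.0058)^20 = 0.89 at 3.0, against (1 − 0.1025)^20 = 0.115 at 3.5.
- Without rounding: 12.9% against 0.8%.

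Same case with within-patient correlation of 0.3 to 0.7 (random intercept):
- Ever below 3.5 falls to 9.0%–6.1%.
- Patients dropped fall to 4.9–3.3 of 58.
- The chance of an empty row at 3.5 in an arm of 20 rises to 15%–28%.

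Range over means 4.2, 4.5 and 4.8 and SDs 0.4, 0.5 and 0.6:
- Patients dropped of 58 run from 0.1 (mean 4.8, SD 0.4) to 22 (mean 4.2, SD 0.6) with independent visits, and from 0.1 to 17.5 with correlation of 0.3 to 0.7.
- At the low end almost every event is missed, but only about 0.2% of patients have one.

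Hyperkalaemia, mean 5.3 and SD 0.5, visits independent:
- 6 or more (true value at least 5.95): p = 0.0968, P(ever) = 0.457.
- More than 6 (true value above 6.05): p = 0.0668, P(ever) = 0.340.
- Difference: 58 × (0.457 − 0.340) = 6.8 patients, or 3.7 to 5.3 with correlation of 0.3 to 0.7. It comes wholly from rounding; on a continuous scale it is zero. Baseline values, which 15.2.4 includes, are not modelled.

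**The case against.** The best defence is that the SAP already specifies the right comparison elsewhere. Row 2.5 of section 8.2 gives the outcome measure as the between-arm difference in the proportion below 3.5, and 15.2.4 asks for the same count. An analyst working from sections 8, 10 and 15 would use 3.5. The Table 6 shell also shows other slips: its column header says exploratory although the table is for safety endpoints, and the table numbers jump from 2 to 5 and from 6 to 10. So 3.0 is probably a clerical error. Affected patients may also appear in the adverse event tables, because a value below 3.5 is a special-interest event and is excepted from the non-reporting rule in protocol 17.6. The numerical illustration rests entirely on assumed inputs, and an arm of 58 is not what the trial obtained, since SAP 12.1 says the planned sample was not reached.

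All of this is fair, and it limits the weight of the point. It does not remove it. A clerical slip in the shell that becomes the published table still yields a wrong count, and the adverse event tables give preferred terms, not a threshold count. The direction of the error, an undercount of low potassium, follows from the text and needs no simulation.

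**Conclusion.** The concern holds. Table 6 carries the wrong threshold for a prespecified safety endpoint, and the likely effect is to under-report a risk of SZC that the protocol itself names. The upper-limit wording in 15.2.4 is a minor mismatch of the same kind, and its omission of the 6.5 count is only an omission, since 8.2, 10.2 and Table 6 keep it.

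The consequence is confined to descriptive safety counts and odds ratios. The primary endpoint and the sample size are untouched, and SAP 13.3 has removed hypothesis testing. With the sample short of plan and testing dropped, however, such counts are a large part of what the trial can report. The patient numbers above are illustrations under assumed distributions and range from negligible to substantial; the textual contradiction does not depend on them. This should be corrected before the table is produced.

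**What to change.** In SAP section 16, Table 6, change 3.0 to 3.5 mmol/L in the low-potassium row. In SAP 15.2.4, define high potassium as higher than 6 mmol/L and, separately, higher than 6.5 mmol/L. Both edits bring the SAP back to the sponsor's own endpoint definition and touch reporting thresholds only.

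The change is one table cell and one phrase, with no new data, assessments or analyses. Because SAP version 1.1 has been signed, it also needs a new version, a line in the revision history and a signature. If results have already been tabulated from the shell, the Table 6 low-potassium row should be re-run at 3.5, and any high-potassium count made under the 15.2.4 wording should be re-run at more than 6.
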